3. *Describe circumstances that may lead to a subject being removed from the trial by the PI, e.g. due to failure to follow study procedures, and the process for doing so:* Since the study involves a one time intra-operative dose of tranexamic acid or placebo, there is no specific study procedure that the patient will be required to follow. Patients will be removed from the trial if the assigned intervention is not available to the operating room staff prior to wound closure.
4. *Describe any stopping rules for the study:* The study will be stopped if an increase in the rate of mortality, pulmonary embolism, deep vein thrombosis, myocardial infarction, cerebrovascular accident, acute renal cortical necrosis, or central retinal artery or vein obstruction is observed. These are considered to be rare events following elective hip hemiarthroplasty. The study stopping rules for these events are described in the following table:

Adverse Event	Stopping Criteria	Reference(s)
Mortality	The 30-day mortality rate following hip hemiarthroplasty has been reported to range from 2.4% to 10.1%. Assuming a conservative estimate of 6.25% mortality and a sample size of 102 patients, we would expect to see 6-7 patient deaths overall during our study period,	The 30-day mortality rate in patients undergoing hip arthroplasty for displaced hip fracture was 2.4% (186 of 7774). Parvizi J, Ereti MH, Lewallen DG. Thirty-day mortality following hip

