	
which begins on the date of surgery and ends 4-6 weeks postoperatively. In each 51 patient subgroup, we would expect to see 3-4 patient deaths over the study period when applying this 6.25% mortality rate. If death occurs in 5 patients in the tranexamic acid subgroup (1 death above the expected), the study will be stopped and an inter-group assessment will occur (see below). If 4 or fewer patient deaths (3 to 4 patient deaths are expected based upon our conservative assessment of the literature) occur in the tranexamic acid subgroup, the study will be continued until completion.
 
It is possible that the placebo group will have a higher number of deaths due to chance, due to our conservative estimate of mortality rate (6.25%) for our study duration, or due to a protective effect from tranexamic acid. Mortality rates following hip hemiarthroplasty are variable. Topical use of tranexamic acid has been associated with a relative risk of 0.28 (95% CI, 0.06 to 1.34; $P = 0.11$) for mortality. If the placebo group has experienced a greater number of deaths than would be expected from our conservative estimate based upon the available literature ($n = 5$ or greater), we will continue the study.
 
If 5 patient deaths (1 above the expected) occur in the tranexamic acid subgroup and 4 or fewer patient deaths have occurred in the placebo subgroup, the study will be stopped.
 
If 5 patient deaths (1 above the expected) occur in the tranexamic acid subgroup and 5 or more deaths have already occurred in the placebo subgroup, we will continue the study. In this instance, the study will either continue to completion or be stopped if at any point the number of deaths in the tranexamic subgroup exceeds that of the control.
	
arthroplasty for acute fracture. J Bone Joint Surg Am. 2004 Sep;86-A(9):1983-8.
 
At one month, 359 out of 3,634 (9.9%) patients receiving a cemented hemiarthroplasty and 1,051 out of 10,362 (10.1%) patients receiving a cementless hemiarthroplasty had died.
 
 
The 90-day mortality rate of patients undergoing hip hemiarthroplasty was 9.8% in patients 65-84 years of age and 18.3% in patients ≥ 85 years of age
 
 
Topical use of the tranexamic acid is associated with relative risk of 0.28 (95% CI, 0.06 to 1.34; $P = 0.11$) for mortality.
 
 
The number of patients who experienced a symptomatic in-hospital pulmonary embolism in

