5. *Additional Comments by PI:* The stopping rules were developed based on the available literature regarding complication rates following hip hemiarthroplasty. While rare, complications including death occur in this population following hip hemiarthroplasty. Additionally, these rates vary from study to study. In developing the stopping criteria we used the conservative estimates of adverse events in an effort to prevent overestimating the true rate of occurrence. Using these estimates we considered both the number needed in the tranexamic group to constitute stopping the study as well as the relative difference between the study groups. Given the heterogeneous nature of the patient population and the variability between institutions reporting these events, we may observe a larger number of occurrences in adverse events in both groups. To account for this potential increase in rates across the entire study cohort, the stopping criteria includes comparisons of the number of events between the two groups. Un-blinded data will be reviewed by an independent data safety monitoring board.

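### The mortality trigger of 5 deaths is called one above expected, but at the row's own hemiarthroplasty rates 5 is the expected count, and the placebo comparison only partly limits false stops (about 19% to 46%)

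*Combined protocol and SAP*

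**What the plan says.** The Mortality row of the stopping-rule table (Combined protocol and SAP, Appendix A, item 4) opens with "The 30-day mortality rate following hip hemiarthroplasty has been reported to range from 2.4% to 10.1" percent. It continues "Assuming a conservative estimate of 6.25% mortality and a sample size of 102 patients" and derives 6-7 deaths overall and 3-4 per arm of 51.

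The trigger follows: "If death occurs in 5 patients in the tranexamic acid subgroup (1 death above the expected), the study will be stopped" for an inter-group assessment. If placebo deaths are then 4 or fewer, the study stops. If placebo already has 5 or more, the study continues, but stops at any later point at which tranexamic acid deaths exceed placebo deaths.

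The reference column of the same row gives the sources:

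- "The 30-day mortality rate in patients undergoing hip arthroplasty for displaced hip fracture was 2.4% (186 of 7774").
- "At one month, 359 out of 3,634 (9.9%) patients receiving a cemented hemiarthroplasty" had died, and "1,051 out of 10,362 (10.1%) patients receiving a cementless hemiarthroplasty had died".
- "The 90-day mortality rate of patients undergoing hip hemiarthroplasty was 9.8% in patients 65-84 years of age and 18.3% in patients" aged 85 or over.

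Item 5 (Additional Comments by PI) says that conservative rates were used so as not to overestimate the true rate. It allows that both groups may have more events than assumed, and adds: "To account for this potential increase in rates across the entire study cohort, the stopping criteria includes comparisons" of event counts between the two groups.

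**The concern.** The low end of a range presented as hemiarthroplasty mortality comes from a source that the row itself does not label hemiarthroplasty. Hemiarthroplasty is the trial's only procedure, and the one-month figures that carry that label are both close to 10%. If mortality is near those figures, a count described as one above expected is simply the expected count, and the rule reacts to background mortality.

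Two things are at stake. A trial of 102 patients with 80% power for its primary outcome could be stopped early on a mortality signal that is only chance. And the data safety monitoring board would work from a description of the rule (one above expected, adjusted for higher rates in both groups) that is more reassuring than the rule's behaviour. The plan gives no false-stop probability at any mortality rate.

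**Working it through.** **Inputs**, all from Appendix A, item 4, Mortality row: 51 patients per arm; assumed rate 6.25%; range ends 2.4% and 10.1%; hemiarthroplasty deaths at one month 359/3,634 and 1,051/10,362; trigger of 5 tranexamic acid deaths with the placebo comparison described above.

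**Step 1: reproduce the plan's figures.** 51 × 0.0625 = 3.19 per arm and 102 × 0.0625 = 6.38 overall. These match the stated 3-4 and 6-7. Also, (2.4% + 10.1%)/2 = 6.25% exactly. The plan does not say how 6.25% was obtained, so the midpoint derivation is an inference.

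**Step 2: expected deaths at the row's hemiarthroplasty figures.**

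- Cemented: 359/3,634 = 9.9%; 51 × 0.099 = 5.05.
- Cementless: 1,051/10,362 = 10.1%; 51 × 0.101 = 5.15.
- Pooled: (359 + 1,051)/(3,634 + 10,362) = 1,410/13,996 = 10.07%; 51 × 0.1007 = 5.14 per arm and 102 × 0.1007 = 10.3 overall.

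**Step 3: false-stop probability.** Let T and C be the deaths so far on tranexamic acid and placebo. The row's clauses together amount to: stop as soon as T ≥ 5 and T > C. With the same death risk p in both arms, three quantities were calculated:

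- the binomial tail P(T ≥ 5 | n = 51, p), which ignores placebo;
- the full rule, by exact recursion over (T, C) with alternating enrolment, 51 per arm, checked after every patient;
- the same condition applied once, to the final totals.

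| p in both arms | Expected deaths per arm | P(T ≥ 5) | Full rule stops | Final totals only |
|---|---|---|---|---|
| 6.25% | 3.19 | 21.2% | 19.4% | 18.1% |
| 8% (illustrative) | 4.08 | 38.7% | 32.7% | 29.0% |
| 9.9% | 5.05 | 57.8% | 44.9% | 37.3% |
| 10.07% | 5.14 | 59.4% | 45.8% | 37.8% |
| 10.1% | 5.15 | 59.6% | 45.9% | 37.9% |

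Enrolment order hardly matters: at 10.1% the full-rule figure is 45.5% to 46.3% across the orders tried, and simulations of 200,000 trials with blocks of 4, blocks of 6 and unrestricted order agree. In simulation at 10.07%, the median stop falls at about patient 69 of 102.

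**Step 4: what the placebo comparison contributes.** From 6.25% to 10.07%, a rule on the tranexamic acid count alone would rise by 59.4 − 21.2 = 38.2 points. The actual rule rises by 45.8 − 19.4 = 26.4 points. At 10.07% the comparison prevents 59.4 − 45.8 = 13.6 points of stopping. So it absorbs part of a higher common rate but leaves the false-stop probability more than doubled (45.8/19.4 = 2.4). The reason is the margin: once T reaches 5, an excess of one death is enough.

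**The case against.** The strongest reply is that nothing was miscalculated. The expected counts follow from 6.25%, and the plan openly calls that rate conservative and says why. A low benchmark makes a safety rule more sensitive, which is a legitimate choice, and the plan sets no false-stop target that it then misses. This stands: the point concerns a mislabelled source and an overstated description, not an arithmetic slip.

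A reader might go further in three ways that the documents do not support.

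- *That the 2.4% comes from unrelated hip arthroplasty and should be discarded.* The row describes it as arthroplasty for displaced hip fracture, which is close to the trial's indication. The documents do not say how many of those 7,774 patients had hemiarthroplasty. They show only that the figure is not labelled as such.
- *That this trial's mortality is about 10%, so that a harmless drug would stop it nearly half the time.* The 9.9% and 10.1% come from one registry source. Exclusions for recent coronary events, prior thromboembolism, chronic renal failure and anticoagulant use may lower the rate, and the row's 9.8% at 90 days for ages 65-84 implies a one-month rate no higher than that in that group. In the other direction, follow-up runs 4-6 weeks, and the row cites 18.3% at 90 days for the oldest patients. The true rate is unknown.
- *That the between-group comparison gives no protection.* At 10.07% it reduces stopping from 59% to 46%, so the protection is partial.

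The full-rule figures also assume that deaths are known in enrolment order and checked continuously. The row's provision for stopping at any point supports frequent checking, but a single look at final totals gives 18% to 38%. Independent review of un-blinded data is planned, yet the row words the stop as mandatory.

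**Conclusion.** The point holds as a mislabelled benchmark and an incompletely described rule. The trigger of 5 is one above the expected range only at 6.25%; at the row's own one-month hemiarthroplasty figures it is the expected count. With no drug effect, the mortality rule stops about 19% of trials at 6.25% and about 45-46% at 9.9-10.1%, or 18% and 38% on final totals. The honest statement is that range, not its upper end. Item 5's statement that the comparison accounts for higher rates in both groups is only partly true.

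These figures rest on equal mortality in both arms, 51 patients per arm, deaths counted in enrolment order, and the mortality row alone. The other six event rows could add to the chance of a false stop. Part of the problem does not depend on the benchmark: even at 6.25% about one null trial in five stops.

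**What to change.** In Appendix A:

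1. Label the 2.4% in the Mortality row as hip arthroplasty for displaced hip fracture, so that text and reference agree.
2. Give expected deaths as a range across the row's sources: about 3.2 per arm at 6.25% to about 5.1 at 10.1% (6.4 to 10.3 overall). Reconcile the description of 5 as one above expected with that range, or delete it.
3. Reword item 5 to say that the between-group comparison accounts only partly for higher rates in both groups. State the mortality rule's false-stop probability at 6.25% and at about 10%, with the monitoring assumptions.
4. Have the sponsor and the data safety monitoring board reconcile the trigger with these figures and record their reasoning. No particular number is proposed here; the balance between false stops and prompt detection of harm is theirs to set.

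The cost is an Appendix A wording amendment and a short calculation for the board, with no extra patients or procedures. The downside is that a less favourable operating characteristic is put on record.

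### The mortality stopping rule directs continuation to completion at 4 or fewer tranexamic acid deaths, whatever the placebo count and however few patients have been treated

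*Combined protocol and SAP*

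**What the plan says.** Appendix A, item 4 opens with a general statement: "The study will be stopped if an increase in the rate of mortality", or of any of the other listed events, is observed. It then refers to a table for the detail.

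The mortality row starts from the planning rate: "Assuming a conservative estimate of 6.25% mortality and a sample size of 102 patients, we would expect to see 6-7 patient deaths overall". Per arm, "In each 51 patient subgroup, we would expect to see 3-4 patient deaths over the study period". From this it sets a trigger of five deaths in the tranexamic acid arm, described as one above the expected number. At five deaths the arms are compared:

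- If there are five tranexamic acid deaths "and 4 or fewer patient deaths have occurred in the placebo subgroup, the study will be stopped".
- If the placebo arm already has five or more deaths, the study goes on. It then stops if tranexamic acid deaths exceed placebo deaths at any later point.

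Below five, the row says that if 4 or fewer deaths "occur in the tranexamic acid subgroup, the study will be continued until completion". The sentence mentions neither the placebo count nor the number treated.

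Item 5 explains that both the count in the tranexamic acid arm and the relative difference between the groups were considered. To allow for higher rates across the whole cohort, "the stopping criteria includes comparisons of the number of events between the two groups". It adds that an independent data safety monitoring board will review unblinded data.

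**The concern.** The between-arm comparison starts only at the fifth tranexamic acid death. Below that the row does more than leave the trigger unmet: it directs that the study continue. The other six rows have no such sentence. They speak of continuing to completion only after their trigger has been reached and the placebo arm has at least as many events.

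The trigger also takes no account of how many patients have been treated. Four deaths among 51 patients and four among the first 15 are handled alike, although the first is close to the planning assumption and the second is far above it. At stake is whether the board may act on an early, one-sided excess of deaths. Item 4's opening statement suggests that an observed increase matters; the mortality row, read literally, says the study goes on.

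**Working it through.** **Inputs.** Mortality 6.25%, cited 30-day range 2.4% to 10.1%, trigger of five deaths (Appendix A, item 4, mortality row); 51 per arm, 102 in total (section 4, sample size).

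**1. The plan's own figures.** Expected deaths = n x rate.

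- Overall: 102 x 0.0625 = 6.375, stated as 6-7.
- Per arm: 51 x 0.0625 = 3.19, stated as 3-4.

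Both reproduce. The rate itself is the midpoint of the cited range: (2.4 + 10.1)/2 = 6.25. The expected count that sets the trigger is therefore a full-arm count.

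**2. The rule in mid-trial.** The row speaks of deaths that have already occurred and of stopping at any point, so it applies throughout accrual. The table gives expected deaths and the binomial probability of 4 or more among n treated in one arm.

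| Treated in the arm | Expected at 6.25% | P(4 or more) at 6.25% | P(4 or more) at 10.1% |
|---|---|---|---|
| 15 | 0.94 | 1.2% | 5.7% |
| 20 | 1.25 | 3.3% | 13.7% |
| 51 | 3.19 | 39.6% | 77.1% |

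Four deaths in 15 is 4/15 = 27%, against a planning rate of 6.25% and a cited maximum of 10.1%. The continue sentence covers this case just as it covers four in 51.

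**3. Between-arm contrasts under the literal rule** (Fisher's exact test).

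| Deaths, tranexamic acid v placebo | Per arm | Difference | One-sided p | Two-sided p | Rule |
|---|---|---|---|---|---|
| 4 v 0 | 15 | 26.7 points | 0.050 | 0.100 | continue |
| 4 v 0 | 51 | 7.8 points | 0.059 | 0.118 | continue |
| 5 v 4 | 51 | 2.0 points | 0.50 | 1.00 | stop |

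The rule stops on the weaker contrast and continues on the stronger one.

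**4. How often.** With 6.25% mortality in both arms, the probability of exactly 4 v 0 at 51 per arm is P(X = 4) x P(X = 0) = 0.1836 x 0.0372 = 0.0068, about 0.7%.

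**The case against.** The strongest reply is that the text describes a two-step gate. The tranexamic acid count must first exceed the expected 3-4; only then does a comparison with placebo decide whether to go on. Item 5 gives the purpose of the comparison as protection against high rates in both arms, so it need not operate below the trigger. On this reading, item 4's opening statement is a lead-in, and the table defines what counts as an increase. The continue sentence merely completes the trigger sentence, and any count threshold produces an odd pair such as 4 v 0 and 5 v 4 at its edge.

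Much of this stands. At full enrolment, continuing at 4 v 0 is consistent with the gate, and the result is not significant. Stopping at 5 v 4 can be defended as deliberate caution. The reply does not cover the period before full enrolment. The gate's first step is a count above expectation, and with 15 treated the expectation is about one death, not 3-4.

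Three stronger readings are tempting, and the documents do not support them:

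- A reader might infer that the row contradicts its own stated basis. Item 5 names the tranexamic acid count as one of two considerations, so tension is the accurate word.
- A reader might infer that the trial as a whole must continue, or that the rule overrides the board. The sentence sits in one row, the other event rows can still stop the study, and nothing bars the board from acting. The gap is that its authority below five deaths is not stated.
- A reader might note that with tranexamic acid mortality doubled to 12.5%, 4 or fewer deaths in 51 has probability 22%, and take that as the size of the problem. It is not the probability of an imbalance, because it ignores the placebo arm.

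**Conclusion.** The point holds as a defect in a stated safety rule. The mortality row alone directs continuation at 4 or fewer tranexamic acid deaths, regardless of placebo deaths and of the number treated. Its expected count applies only to a full arm of 51, so early in the trial it directs continuation in situations that item 4's opening statement would naturally treat as an observed increase in mortality. It also sits uneasily with item 5's reference to the relative difference between the groups.

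The size is modest in frequency: a final 4 v 0 occurs in about 0.7% of trials at 6.25% in both arms. The numbers do not show that continuing at 4 v 0 would be wrong at full enrolment. The case for acting rests on the outcome being death and on the ambiguity about the board's role.

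The calculations assume independent deaths at a constant rate, complete follow-up of those counted as treated, and equal numbers per arm. The 15 and 20 per arm are illustrations; the protocol names no interim look.

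**What to change.** Reconcile the opening statement of Appendix A, item 4, the mortality row and item 5 on whether an imbalance below five tranexamic acid deaths is assessed. In the mortality row, remove the unconditional direction to continue to completion, so that 4 or fewer deaths means only that the five-death trigger has not been met. State, there or in the board's charter, that the board reviews deaths by arm together with the number treated in each arm, and that it is not bound to continue when the trigger is unmet.

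What difference between arms should prompt action is for the board and the sponsor to decide; no threshold is proposed here. The cost is about one sentence in the table and matching text for the board. It needs no extra patients, visits or data, since deaths and treatment assignment are already recorded.
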